2.0 OBJECTIVES

2.1 Primary Objective

To determine whether patient-specific mutations correlate with clinical overall response to decitabine in patients with AML or MDS.

2.2 Secondary Objectives

- To determine whether 10 consecutive days per cycle of decitabine improves outcomes compared with historical controls treated with 5 consecutive days per cycle of decitabine.
- To determine whether other biomarkers correlate with clinical overall response to decitabine in patients with AML or MDS. These will include:
 1. The velocity and depth of patient-specific mutation clearance;
 2. The bone marrow expression profile and change in expression profile during decitabine treatment;
 3. The steady-state plasma decitabine concentrations;
 4. The decrease in bone marrow methylcytosine content in response to decitabine.

3.0 PATIENT SELECTION

3.1 Inclusion Criteria

One of the following:

- Patient must have non-M3 AML and be ≥ 60 years of age OR
- non-M3 AML with relapsed disease OR
- Symptomatic MDS with one of the following:
 - Symptomatic anemia with either hemoglobin < 10.0 g/dL or requiring RBC transfusion
 - Thrombocytopenia with a history of two or more platelet counts $< 50,000$ /mcL or a significant hemorrhage requiring platelet transfusions
 - Neutropenia with two or more ANC $< 1,000$ /mcL

All of the following:

1. Patient must have an ECOG performance status ≤ 2 .
2. Patient must have $>10\%$ disease burden measured by cytomorphology, flow cytometry, or cytogenetics.
3. Patient must have peripheral white blood cell count $\leq 50,000$ /mcl.
4. Patient must have adequate organ function, defined as:
 - a. Total bilirubin ≤ 1.5 x ULN
 - b. AST/ALT ≤ 2.5 x ULN
 - c. Serum creatinine ≤ 2.0 x ULN
5. Patient must have undergone ≤ 2 cycles of prior hypomethylating agent (decitabine or azacitidine).
6. Patient must be enrolled in HRPO# 201011766 (“Tissue Acquisition for Analysis of Genetic Progression Factors in Hematologic Diseases”).
7. Patient must be ≥ 18 years of age.
8. Patient must be able to understand and willing to sign an IRB-approved written informed consent document.

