Because all patient-specific exome-discovered mutations will be assessed a second time in the primary bone marrow sample as well as the Cycle 1 Day 10 \pm 1, Cycle 1 Day 28 \pm 4, and Cycle 2 Day 28 \pm 4 bone marrow samples, this study will also serve to validate all exome-discovered mutations. This is important, because exome sequencing is associated with a 20-50% false-discovery rate depending on type I error tolerated (mutation-calling algorithms are typically set for greater sensitivity than specificity). Thus, many mutations discovered during exome sequencing are incorrect. This second analysis of these mutations will server to exclude these false positive calls.

3. To correlate the bone marrow expression profile from pre-study and Cycle 1 Day 10 \pm 1 with response to decitabine.

We will correlate expression signatures, and changes in expression signatures, with:

- Achievement of clinical CR,
- Mutation status.

4. To correlate steady-state plasma decitabine concentration on Cycle 1 Day 4 \pm 1 with:
 - Achievement of CR.

5. To correlate the extent of bone marrow DNA hypomethylation on Cycle 1 Day 10 \pm 1 with response to decitabine.

We will assess the percent reduction in bone marrow methylcytosine content using LC-MS. Patients will be evaluated pre-study and Cycle 1 Day 10 \pm 1. The change in DNA methylcytosine content will be correlated to:

- Achievement of clinical CR,
- Change in expression signature.

This will determine whether inadequate blast exposure to decitabine correlates with drug resistance.

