3.2 Exclusion Criteria

1. Patient must not be pregnant or nursing.
2. Patient must not have known CNS leukemia.
3. Patient must not have a history of positive HIV serology.
4. Patient must not have a history of positive Hepatitis C serology.
5. Patient must not have undergone a prior allogeneic stem cell transplant.
6. Patient must not have any uncontrolled intercurrent illness including, but not limited to, ongoing or active infection, ongoing or active GVHD, congestive heart failure of NYHA class 3 or 4, unstable angina pectoris, cardiac arrhythmia, or psychiatric illness/social situation that would limit compliance with study requirements.
7. Patient must not have had radiation therapy within 14 days of enrollment.
8. Patient must not have received any chemotherapy within 21 days of enrollment, and any acute treatment-related toxicities must have returned to baseline. Patients

may be receiving hydra at time of enrollment.

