5.2 Study Procedures

5.2.1 Pre-study Procedures

Pre-study procedures must take place no more than 14 days prior to the first dose of decitabine except where noted below.

1. Bone marrow aspirate and biopsy. Standard bone marrow procurement procedures will be followed for collection of the tissue. Assessments performed on bone marrow will include correlative studies (collected under HRPO# 201011766), morphologic assessment, cytogenetics, and FISH.
2. Bone marrow or peripheral blood for flow cytometry
3. Skin biopsy sample (collected under HRPO# 201011766). There is no required time frame for this sample; it may have been collected months or even years prior to the first dose of decitabine.

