5.4 Concomitant Therapy and Supportive Care Guidelines

5.4.1 Chemotherapy

Patients cannot receive any chemotherapy within 21 days of study enrollment and must have recovered from any treatment-related toxicities. However, patients may be receiving hydrea at enrollment and may continue on hydrea through Cycle 2 of decitabine. An indication for hydrea following 2 cycles of decitabine is evidence that the patient is not responding and decitabine should be discontinued. Other than decitabine, patients cannot receive chemotherapy during this trial.

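### Pretreated patients may give their baseline marrow as little as 7 days after a hypomethylating dose, and the analyses do not separate them from untreated patients

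*Combined protocol and SAP*

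**What the plan says.** Section numbers refer to the current version in the file, whose statistical section is 14.

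- **Eligibility (3.1).** Up to two "cycles of prior hypomethylating agent (decitabine or azacitidine") are allowed. No washout specific to these agents is given.
- **Washout (3.2).** "Patient must not have received any chemotherapy within 21 days of enrollment". Section 5.4.1 implies that decitabine counts as chemotherapy: "Other than decitabine, patients cannot receive chemotherapy during this trial".
- **Marrow window (5.2.1).** "Pre-study procedures must take place no more than 14 days prior to the first dose of decitabine except where noted below". The exception noted there is the skin sample. Nothing ties the marrow to the end of earlier treatment.
- **Use as baseline (1.3).** The pre-study marrow is the tumor sample for exome sequencing, the starting point for allele-frequency clearance and the comparator for expression change. For methylation: "We will assess the percent reduction in bone marrow methylcytosine content using LC-MS. Patients will be evaluated pre-study and Cycle 1 Day 10".
- **Schedule comparison (2.2, 14.2.3).** One aim is to learn whether the 10-day schedule "improves outcomes compared with historical controls treated with 5 consecutive days per cycle of decitabine". The control is reference 2, a phase II study described by its title as first-line treatment in older AML patients.
- **Cycle counting (9.4.1, 14.2.3).** Treatment failure, and the response grouping used for clearance, are judged after four study cycles.
- **Handling of prior exposure.** It defines no population in 14.1 and no subgroup in 14.2.5. Section 14.2.2 plans a logistic model adjusting for unspecified demographic and clinical characteristics and does not name it.

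**The concern.** The baseline-dependent measures treat the pre-study marrow as a pre-drug state. For a patient who recently had decitabine or azacitidine, it may not be one. The plan itself looks for drug effect on methylcytosine and expression by Day 10, and on allele frequency at Days 10, 28 and 56. A marrow taken 7 days after earlier drug falls inside the period in which the plan expects the drug to be acting.

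Methylcytosine has most at stake. Section 1.3 intends to use the reduction to judge whether poor response reflects too little drug reaching the blasts. A baseline already altered by earlier drug could change the measured reduction for a different reason. If prior exposure is also related to response, pooling exposed and unexposed patients biases the comparison of responders with non-responders.

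The second issue needs no carry-over assumption. A pretreated patient's response follows the earlier cycles plus the study cycles, but is credited to the 10-day schedule and compared with a first-line control.

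**Working it through.** **1. Shortest permitted gap.** Let k be the days from enrollment to first dose, and m the days from marrow to first dose (0 to 14).

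Gap from last dose to marrow = 21 + k - m.

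- m = 14, k = 0: 21 + 0 - 14 = 7 days
- m = 14, k = 3: 10 days
- m = 14, k = 7: 14 days
- m = 0: 21 + k days

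If a site did not count a hypomethylating agent as chemotherapy, no minimum would apply. The bar in Section 4.0 on starting protocol interventions before registration does not close the gap, because the correlative marrow is collected under a separate tissue protocol.

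**2. Cycle count.** 2 prior + 4 study cycles = up to 6 cycles at the 4-cycle assessment.

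**3. The plan's methylcytosine power (14.2.3).** Inputs: 45 responders, 55 non-responders, difference 20 points, SD 15, alpha 0.05 (taken as two-sided).

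Standard error = 15 × √(1/45 + 1/55) = 3.02; 20/3.02 = 6.6. Noncentral-t power is above 99.99%. The stated 99% is met with room to spare, so lack of power is not the issue.

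**4. Dilution (assumption).** Suppose a share f of patients shows no between-group difference because of a carried-over baseline. The difference becomes 20 × (1 - f).

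| f | Difference | Power |
|---|---|---|
| 10% | 18 | >99.9% |
| 20% | 16 | >99.9% |
| 30% | 14 | 99.6% |

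**5. Bias (illustration only).** Suppose prior exposure differs by 20 percentage points between responders and non-responders and shifts the measured reduction by 11 to 22 points. The 11 and 22 are the reductions reported for a shorter and a 10-day course in Section 1.2.2 of an earlier protocol version in the file; that section is redacted in the current one. The spurious difference is 0.20 × 11 = 2.2 to 0.20 × 22 = 4.4 points. With the standard error above, a nominal 5% test then rejects a true null about 11% to 30% of the time. Neither the imbalance nor the shift is documented, and the sign could go either way.

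**6. Cost of restricting to unexposed patients.** The share pretreated is not given; assume 10%, 20% or 30%. The 100 evaluable patients become 90, 80 or 70, and methylcytosine power remains above 99.9% in each case. Section 14 gives no power figure for the 10-day versus 5-day comparison, so the loss there can only be stated as a count.

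**The case against.** The strongest reply is that 7 days is a corner case. It needs a last dose exactly 21 days before enrollment, study treatment on the enrollment day, and a marrow at the far edge of its window. A marrow on the day of first dose is at least 21 days out. This stands, and limits the point to what the plan permits.

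Four stronger readings are tempting, and the documents do not support them.

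- **That the washout is too short because it is less than a 28-day cycle.** The 21 days run from the last dose, while a cycle includes dosing days. The plan's schedule leaves 28 - 10 = 18 drug-free days, and a 5-day schedule 23. The comparison is not like for like.
- **That the measured methylcytosine reduction must shrink by a calculable amount.** This requires an assumed persistence and a fixed Day 10 level that treatment cannot go below. If study drug instead removes a constant proportion of what is present, a 22% reduction is measured as 22% whatever the carry-over. The plan supports neither model over the other.
- **That pretreated patients will show slower clearance.** Velocity is a log rate; under log-linear decline, the slope does not depend on the starting allele frequency. Distortion is possible, but its direction is not established.
- **That reduced clones will be called wild-type in the primary analysis.** Entry requires more than 10% disease burden, and the recurrently mutated genes, including the four of main interest, are also assessed by targeted capture. At most this is a concern for minor clones.

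It can also be said that the planned logistic model could include prior exposure, since medical history is collected. It could, but nothing commits the analysis to it, and the model does not cover the methylcytosine, expression-change or clearance comparisons. Finally, the trial also admits relapsed AML and MDS, so excluding pretreated patients would not by itself make the first-line control comparable.

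**Conclusion.** The concern holds in a limited form. The plan allows a baseline marrow as little as 7 days after a hypomethylating dose, uses it as the reference for methylcytosine, expression change and clearance, and pools these patients with unexposed ones. It also allows up to six total cycles at a 4-cycle assessment compared with a first-line control. The 7-day figure assumes that hypomethylating agents fall under the 21-day chemotherapy rule, as Section 5.4.1 implies.

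The result is a risk of bias in secondary analyses, of unknown size and direction. The visible text documents neither how long the drug effect lasts nor how many patients are pretreated, and parts of the background are redacted. The 11-30% error rate is a what-if, not an estimate. This is a cheap improvement worth making, not a defect that undermines the primary analysis.

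**What to change.** 1. **Data.** Record prior hypomethylating exposure (agent, number of cycles) and the days from last dose to the pre-study marrow.
2. **Section 14.2.3.** Pre-specify the methylcytosine, expression-change, clearance and 10-day versus 5-day analyses in patients with no prior hypomethylating agent, and show pretreated patients separately.
3. **Section 14.2.2.** Enter prior exposure (none versus 1-2 cycles) in the planned logistic model. All patients stay in the primary analysis.
4. **Section 5.2.1.** Where the schedule allows without a repeat biopsy, take the single correlative marrow in pretreated patients late in the 14-day window. The 21-day and 14-day rules should be reconciled with the use of this marrow as baseline. No clinical washout is proposed here.

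The cost is two data items, a few sentences in the plan and somewhat fewer patients in those secondary analyses. Where the eligibility marrow has already been taken early in the window, the sample stays as it is and the recorded interval shows it.

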3.2 Exclusion Criteria

1. Patient must not be pregnant or nursing.
2. Patient must not have known CNS leukemia.
3. Patient must not have a history of positive HIV serology.
4. Patient must not have a history of positive Hepatitis C serology.
5. Patient must not have undergone a prior allogeneic stem cell transplant.
6. Patient must not have any uncontrolled intercurrent illness including, but not limited to, ongoing or active infection, ongoing or active GVHD, congestive heart failure of NYHA class 3 or 4, unstable angina pectoris, cardiac arrhythmia, or psychiatric illness/social situation that would limit compliance with study requirements.
7. Patient must not have had radiation therapy within 14 days of enrollment.
8. Patient must not have received any chemotherapy within 21 days of enrollment, and any acute treatment-related toxicities must have returned to baseline. Patients

may be receiving hydra at time of enrollment.

3.3 Inclusion of Women and Minorities

Both men and women and members of all races and ethnic groups are eligible for this trial.

4.0 REGISTRATION PROCEDURES

Patients must not start any protocol intervention prior to registration through the Siteman Cancer Center.

The following steps must be taken before registering patients to this study:

1. Confirmation of patient eligibility by Washington University
2. Registration of patient in the Siteman Cancer Center database
3. Assignment of unique patient number (UPN)

Once the patient has been entered in the Siteman Cancer Center database, the WUSM coordinator will forward verification of enrollment and the UPN via email.

4.1 Confirmation of Patient Eligibility

Confirm patient eligibility collecting the information listed below and scanning and emailing it to the research coordinator listed in the *Siteman Cancer Center Clinical Trials Core Protocol Procedures for Secondary Sites* packet at least one business day prior to registering patient:

1. Your name and contact information (telephone number, fax number, and email address)
2. Your site PI's name, the registering MD's name, and your institution name
3. Patient's race, sex, and DOB
4. Three letters (or two letters and a dash) for the patient's initials
5. Currently approved protocol version date
6. Copy of signed consent form (patient name may be blacked out)
7. Planned date of enrollment
8. Completed eligibility checklist, signed and dated by a member of the study team
9. Copy of appropriate source documentation confirming patient eligibility

4.2 Patient Registration in the Siteman Cancer Center Database

Registrations may be submitted Monday through Friday between 8am and 5pm CT. Urgent late afternoon or early morning enrollments should be planned in advance and coordinated with the Washington University research coordinator. Registration will be confirmed by the research coordinator or his/her delegate by email within one business day. Verification of eligibility and registration should be kept in the patient chart.

All patients at all sites must be registered through the Siteman Cancer Center database at Washington University.

4.3 Assignment of UPN

Each patient will be identified with a unique patient number (UPN) for this study. Patients will also be identified by first, middle, and last initials. If the patient has no middle initial, a dash will be used on the case report forms (CRFs). All data will be recorded with this identification number on the appropriate CRFs.

5.0 INVESTIGATIONAL PLAN

5.1 Summary of Study Design

This is an open-label, single-arm, Phase II, biomarker study of patients with AML or MDS who are treated with 10 consecutive days of decitabine. FAB-M3 AML is excluded from this trial, because other well-tolerated options exist for the treatment of FAB-M3 acute promyelocytic leukemia. AML patients who are < 60 years old and have not received cytotoxic induction chemotherapy are also excluded, because cytotoxic therapy offers a curative possibility for these patients. MDS patients without cytopenias are also excluded because these patients can be followed with watchful-waiting.

All patients will undergo bone marrow biopsies pre-study, on Cycle 1 Day 10 \pm 1, and on Day 28 \pm 4 of Cycles 1, 2, 4, and 6. Following Cycle 6, bone marrow biopsies should be performed at the discretion of the treating physician to assess for relapse or progression. Patients will provide a skin biopsy sample pre-study. Patients will also provide peripheral blood samples on Cycle 1 Day 4 \pm 1 for pharmacokinetic studies. See Section 8.0 for details on correlative studies.

Patients will receive decitabine 20 mg/m²/day as a 1-hour infusion on consecutive Days 1-10 in 28-day cycles. The dose will be calculated based on actual patient weight at the beginning of each cycle.

Once AML patients achieve morphologic complete remission with incomplete blood count recovery (CRi) or MDS patients achieve a marrow complete response (Marrow CR) as defined in Section 9.0, decitabine administration may be decreased to five consecutive days to limit myelosuppressive toxicity at the discretion of the treating physician. After two cycles of five consecutive days of treatment, if the patient meets the definition of CR with complete cytogenetic response as defined in Section 9.0, administration may further be decreased to three consecutive days per cycle at the discretion of the treating physician.

It will be a logistical goal of this trial consistently to return preliminary exome results to the treating physician by the end of Cycle 1 and validated results by the end of Cycle 2. However, this logistical goal is not a primary or secondary aim of this study. Given the limited data regarding mutation presence and drug response, we do not anticipate that the results will directly influence therapeutic decisions made by the treating physician. However, the development of comprehensive genomic pipelines and integration of this data into a clinical trial setting will be required before personalized medicine can be realized.

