Patients with progressive disease after two cycles (defined as a clear increase in bone marrow blast count, typically a > 50% increase in bone marrow blasts over baseline) should be removed from study.

Patients with stable disease may continue on study and should undergo a diagnostic bone marrow biopsy at the end of even numbered cycles.

Once AML patients achieve morphologic complete remission with incomplete blood count recovery (CRi) or MDS patients achieve a marrow complete response (Marrow CR) as defined in Section 9.0, decitabine administration may be decreased to 20 mg/m²/day for ten consecutive days every 6 weeks, to limit myelosuppressive toxicity and improve count recovery. After 2 cycles at 6 week intervals, the dose may be reduce to 20 mg/m²/day for five consecutive days in 6 week cycles, at the discretion of the treating physician. After two cycles of five consecutive days of treatment, if the patient meets the definition of CR with complete cytogenetic response as defined in Section 9.0, administration may further be decreased to three consecutive days per cycle at the discretion of the treating physician.

Sample collection for correlative studies:

Bone marrow biopsies should be performed at baseline, at Cycle 1 Day 10 ± 1, and at Day 28 ± 4 of Cycles 1, 2, 4, and 6. Following Cycle 6, bone marrow biopsies should be performed at the discretion of the treating physician to assess for relapse or progression.

Peripheral blood samples should be collected on Day 4± 1 of Cycle 1. Collection should be obtained 45 ± 15 minutes after decitabine infusion is initiated.

Genomic Predictors of Decitabine Response in AML/MDS

Table of Contents

Section	Page
Section 4.21.0 INTRODUCTION	7
1.1 Rationale.....	7
1.2 Decitabine and Hypomethylating agents in AML/MDS.....	9
1.2.1 Pharmacokinetics and Metabolism of Decitabine.....	11
1.2.2 Experience with extended dosing schedules.....	12
1.3 Correlative Studies	13
2.0 OBJECTIVES.....	15
2.1 Primary Objective.....	15
2.2 Secondary Objectives	15
3.0 PATIENT SELECTION.....	16
3.1 Inclusion Criteria	16
3.2 Exclusion Criteria.....	16
3.3 Inclusion of Women and Minorities.....	17
4.0 REGISTRATION PROCEDURES	18
4.1 Confirmation of Patient Eligibility.....	18
4.2 Patient Registration in the Siteman Cancer Center Database.....	18
4.3 Assignment of UPN.....	18
5.0 INVESTIGATIONAL PLAN	20
5.1 Summary of Study Design.....	20
5.2 Study Procedures	20
5.2.1 Pre-study Procedures.....	20
5.2.2 Baseline Evaluation.....	21

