6.3 Modification in Dose or Schedule for Treatment Response

Once AML patients achieve morphologic complete remission with incomplete blood count recovery (CRi) or MDS patients achieve a marrow complete response (Marrow CR) as defined in Section 9.0, decitabine administration may be decreased to 20 mg/m²/day for ten consecutive days, and the cycles may be administered every 6 weeks to limit myelosuppressive toxicity, at the discretion of the treating physician. After two cycles at six week intervals, the dose may be reduced to 20 mg/m²/day for five consecutive days of treatment in six week intervals. If the patient meets the definition of CR with complete cytogenetic response as defined in Section 9.0, administration may further be decreased to three consecutive days per cycle at the discretion of the treating physician.

[Redacted]

[Redacted]

[Redacted]

[Redacted]

[Redacted]

[Redacted]

[Redacted]

[Redacted]

[Redacted]

[Redacted]

[Redacted]

[REDACTED]

[REDACTED]

[REDACTED]

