^h Decitabine treatment will be 20 mg/m² over a 1-hour IV infusion on consecutive Days 1-10 every 28-day cycle. The dose will be calculated based on actual patient weight at the beginning of each cycle. Patients may be premedicated with lorazepam, prochlorperazine, palonosetron, or ondansetron at the treating physician's discretion.

ⁱ Patients will be followed for 30 days following the date of the last decitabine dose to monitor for toxicity, survival and response. Thereafter, the investigator or designee will record information on subsequent therapy, disease progression, and death, every 6 months for 2 years after first dose of study drug or until the patient is lost to follow-up.

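### Section 5.1 contradicts Section 6.3 and the Study Schema on the decitabine schedule after response; this exposes post-response outcomes, not the initial 10-day treatment

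*Combined protocol and SAP*

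**What the plan says.** All references are to the protocol version with secondary sites, multicenter Section 13.0 and statistics in Section 14.0.

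- **Starting schedule, Section 5.1:** "Patients will receive decitabine 20 mg/m²/day as a 1-hour infusion on consecutive Days 1-10 in 28-day cycles". No section disagrees.
- **Trigger for a change:** CRi in AML or Marrow CR in MDS, in Section 5.1, the Study Schema and Section 6.3 alike.
- **First step, Section 5.1:** "decitabine administration may be decreased to five consecutive days to limit myelosuppressive toxicity at the discretion of the treating physician". No interval other than 28 days is mentioned.
- **First step, Study Schema:** "decitabine administration may be decreased to 20 mg/m²/day for ten consecutive days every 6 weeks".
- **First step, Section 6.3:** "decitabine administration may be decreased to 20 mg/m²/day for ten consecutive days, and the cycles may be administered every 6 weeks".
- **Second step, Schema and Section 6.3:** five days, still every 6 weeks, after two 6-week cycles.
- **Three-day step:** Section 5.1 and the Schema require two 5-day cycles plus CR with complete cytogenetic response. Section 6.3 begins the condition with "If the patient meets the definition of CR with complete cytogenetic response" and sets no minimum number of 5-day cycles.
- **Flow chart (Appendix 2):** footnote 3 permits Days 1-5 or 1-3, refers to Section 6.3 and does not mention 6-week cycles. Footnote h gives treatment "on consecutive Days 1-10 every 28-day cycle". Footnote d, like Section 5.2.9, moves the marrow to day 42 ± 4 for responders on 6-week cycles.

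No text states which section prevails. Section 13.0 has every institution work from the same protocol document.

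**The concern.** At the moment of response, the options open to a physician depend on the section consulted. An immediate change to five days in a 28-day cycle is allowed by Section 5.1 but does not follow the sequence in Section 6.3 or the Schema. Section 10.5 requires planned deviations to be approved in advance, so sites and auditors need to know which sequence is the protocol. Section 14.3 plans a further 100 patients with at least two more centers, so sites could settle on different readings.

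The outcomes at stake are those that develop after the trigger:

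- the morphologic CR rate, named as a secondary endpoint in Section 9.0, because a patient in CRi may still convert to CR;
- MDS patients in Marrow CR. Section 14.2.3 counts CR, CRi and PR, and Marrow CR is not listed, so such a patient can change schedule before becoming a counted response;
- remission duration and event-free survival (Section 9.4), and the exposure and by-cycle safety summaries (Section 14.2.4);
- the mutation-clearance analysis, set at 10, 28 and 56 days in Section 14.2.3, if the Cycle 2 marrow moves for responders only.

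**Working it through.** The plan gives no figure for this point. The contradiction rests on setting the texts side by side; its size follows from counting dosing days.

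**Side by side, from CRi or Marrow CR onward**

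| Step | Section 5.1 | Study Schema | Section 6.3 |
|---|---|---|---|
| First change | 5 days; only 28-day cycles named | 10 days every 6 weeks | 10 days every 6 weeks |
| Second change | none stated | 5 days every 6 weeks, after two 6-week cycles | same as Schema |
| Two 5-day cycles required before 3 days | yes | yes | no |

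There are therefore two different first steps, and Section 6.3 and the Schema also disagree with each other on the three-day step.

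**Dosing days after response**

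Inputs: 20 mg/m² per dosing day, and the cycle lengths and days per cycle above. Assumptions: no delays, every reduction taken as soon as it is allowed, a 28-day interval under Section 5.1, and no three-day step. Formula: dosing days = sum of days per cycle over the cycles that fit in the window; dose = 20 × dosing days.

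| Window | Section 5.1 | Section 6.3 and Schema |
|---|---|---|
| 12 weeks | 3 × 5 = 15 (300 mg/m²) | 2 × 10 = 20 (400 mg/m²) |
| 24 weeks | 6 × 5 = 30 (600 mg/m²) | 10 + 10 + 5 + 5 = 30 (600 mg/m²) |
| 36 weeks | 9 × 5 = 45 (900 mg/m²) | 10 + 10 + 4 × 5 = 40 (800 mg/m²) |

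Section 5.1 starts lower, is level at 24 weeks and is higher at 36 weeks.

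**Sensitivity: three-day step taken as soon as allowed** (under Section 6.3, assumed after one 5-day cycle)

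| Window | Section 5.1 | Section 6.3 | Schema |
|---|---|---|---|
| 12 weeks | 5 + 5 + 3 = 13 | 20 | 20 |
| 24 weeks | 5 + 5 + 4 × 3 = 22 | 10 + 10 + 5 + 3 = 28 | 10 + 10 + 5 + 5 = 30 |
| 36 weeks | 5 + 5 + 7 × 3 = 31 | 10 + 10 + 5 + 3 × 3 = 34 | 10 + 10 + 5 + 5 + 2 × 3 = 36 |

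Here Section 5.1 stays lower throughout, by 7 days at 12 weeks, 6 to 8 at 24 weeks and 3 to 5 at 36 weeks.

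**Marrow timing**

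For a patient in response after Cycle 1, the Cycle 2 marrow falls at about 28 + 28 = day 56 on 28-day cycles, but at about 28 + 42 = day 70 if 6-week cycles start at once. Non-responders stay at about day 56.

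**Which response rates can move**

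In AML the trigger is CRi, which already counts in both rates compared with historical controls in Section 14.2.3 (CR/CRi/PR and CR/CRi). A later upgrade from CRi to CR changes neither; it changes only the morphologic CR rate taken alone. In MDS the trigger is Marrow CR, which is in neither list, so a later CR would add a counted response.

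**The case against.** The strongest reply is that Section 5.1 is a summary, the flow chart sends the reader to Section 6.3, and every reduction is optional. In part this stands. Remaining on ten days every 28 days breaches none of the texts, footnote h can be read as the starting schedule only, and exposure after response would still vary by physician once the wording is aligned. Cumulative exposure, intensity and by-cycle safety summaries are already planned. But no text makes Section 6.3 prevail, relying on it leaves its conflict with the Schema on the three-day step, and discretion operates only among permitted options, which differ here.

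A reader might infer three stronger things.

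- **That the 10-day regimen under test is not one regimen.** The documents do not support this: all sections give the same treatment until CRi or Marrow CR.
- **That the comparison of ten with five days per cycle is contaminated.** For AML this does not follow, because the change is triggered by a response already counted in both compared rates. MDS patients in Marrow CR are the exception, and the plan gives no expected number of them.
- **That Section 6.3 gives one third more drug.** That is the 12-week figure alone (20 against 15 days); without the three-day step the difference is gone at 24 weeks and reversed at 36.

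The file reviewed is the second of two parts, so a later and perhaps reconciled version may sit in the part not shown. In the preceding version in this file, the Schema and Sections 5.1 and 6.3 agreed on five days, which suggests that Section 5.1 was left unchanged when the other two were revised.

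**Conclusion.** The contradiction is real within this protocol version and needs correcting, because it concerns dosing text for several centers. Its statistical reach is limited to the course after response. AML responses already counted as CR or CRi stand, and the historical comparison of CR/CRi and CR/CRi/PR is largely unaffected for AML.

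Without the three-day step, the difference between the schedules is 5 dosing days (100 mg/m²) at 12 weeks, none at 24 weeks, and 5 in the other direction at 36 weeks. For a patient responding after Cycle 1 who moves to 6-week cycles, the Cycle 2 marrow comes about 14 days later. These figures assume no delays and the earliest permitted reductions. The effect on the morphologic CR rate, on MDS responses and on the time-to-event measures cannot be sized from the documents, because neither the number of MDS patients nor how often the reductions would be used is given.

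**What to change.** The investigators should reconcile Section 5.1, the Study Schema, Section 6.3 and flow-chart footnotes 3 and h into one sequence, covering days per cycle, cycle length and the condition for the three-day step. No view is taken here on which sequence is right. If a later version already does this, the point is closed for that version.

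In the analysis plan, identify responses upgraded after a schedule change (CRi to CR in AML, Marrow CR to CR in MDS) within the existing response and exposure summaries. A separate table of CR/CRi first reached after a change would be nearly empty for AML, since CRi is itself the trigger.

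The cost is a wording amendment with the usual site approvals, plus a flag in planned output. Section 15.0 already lists Treatment Record and Dose Modifications forms; it does not list their fields, so check that they capture days given and cycle interval.
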